4.2 Screening

Eligible patients will be screened by dedicated protocol study team staff for fulfillment of eligibility criteria as described in Sections 3.1 (Inclusion Criteria) and 3.2 (Exclusion Criteria). If the patient is deemed eligible, protocol consent will then be obtained. Enrollment will proceed as described in Section 3.3. Data collection and storage procedures are described in 15.5

4.3 Prostate Bed Biopsy

In cases when the post-treatment MRI identifies a suspicious lesion, the treating physician will recommend a US-guided biopsy (typically 2-2.5 years post-treatment). The specifications for this biopsy are described below.

As per the discretion of the urologist, prior to biopsy collection, antibiotic prophylaxis may be prescribed (e.g. Levaquin 500 mg daily, Ciprofloxacin 500 mg twice daily, or a similar antibiotic depending on allergy history and physician preference), will be delivered for five days beginning the day before the procedure. Other antibiotic treatment may be administered as part of the biopsy procedure. Aspirin, anticoagulants and vitamin supplements will be temporarily discontinued at least one week prior to the procedure. Therapy may be restarted per standard practice for prostate bed biopsies (typically a day later if there is no bleeding). All patients will be placed in the left lateral decubitus position. Immediately prior to the procedure, 10 cc of 1% Lidocaine will be injected into the bed under ultrasound guidance, typically using a 22 gauge 7-inch needle. The syringe will be aspirated before the lidocaine injection to prevent unintentional injection into the vascular compartment. An ultrasonographic wheal will be viewed in the sagittal plane between the rectal wall and base of the seminal vesicles.

For patients who undergo prostate bed targeted biopsies, (the actual number of cores collected will depend on the size of the lesion. Transrectal ultrasound biopsies will be performed using spring-loaded biopsy gun with an 18 gauge Tru-cut biopsy needle or a similar device. The procedure will be performed by a urologist in the Department of Urology at University of Miami Medical School of Medicine using the ArtemisTM system (Eigen Inc., Grass Valley, California) for US biopsies or other dedicated MRI guided biopsy device. The image fusion system which may be utilized with the Artemis system is FDA approved and is being utilized to localize biopsies for research purposes only. Every attempt will be made to collect at least one biopsy within the area of the tumor, as indicated by MRI, using standard methods for a prostate bed biopsy. During the course of the procedure, hemorrhage may be visualized within the bladder following needle biopsy. If this is the case, or if gross blood is noted at the urethral meatus, bladder catheterization and clot irrigation may be indicated, as determined by the urologist. The biopsies will be paraffin embedded in pathology per routine procedure.

4.4 CT-Simulation

The MRI (Section 4.1) will be fused to the CT-simulation scan. CT-simulation will then be obtained under the same conditions with typical pelvic immobilization. Images will be taken at 1.5 mm intervals from the top of the sacrum to 1 cm below the ischial tuberosities (to include the entire bladder and rectum). All patients will have tattoos placed at the anterior, right lateral, and left lateral isocenter skin points. Patients are instructed to use a rectal enema prior to coming into the department for simulation, which is part of the routine procedures.

4.5 Normal Tissue Contouring Guidelines

Normal tissues will be outlined as solid structures, including the rectum, bladder and femoral heads. The penile bulb will be outlined as a reference structure. No constraints will be placed on the penile bulb, but doses will be recorded. The rectum will be outlined from the anterior flexion of the rectosigmoid superiorly to the ischial tuberosities inferiorly. The bladder and contents will be contoured. The femoral heads should be outlined down to the region between the greater and lesser trochanters.

The potential bowel space within 5 cuts of the CTV should be outlined to minimize dose to the bowel. The potential bowel space includes the areas on either side of the bladder medially.

4.6 Prostate Bed Conformal PTV Planning and Constraints

Patients will be randomized to one of two study arms as described in Section 3.3. Image-guided technique will be used to deliver the fractionation treatments to minimize the dosimetric error. The Clinical Target Volume (CTV), will include the Prostate/SV bed (with MRI GTV). The Planning Target Volume (PTV) will

be 7 mm around the CTV in all dimensions. All patients will be treated with IMRT. The isodose level of the prescription dose shall be kept to 85% or higher, covering the clinical target volume (CTV: prostate bed) plus a planning target volume (PTV) for uncertainty of 7 mm everywhere, except posteriorly, where the margin would be an average 7 mm (6 – 8 mm is acceptable). The pelvic lymph may be treated to a dose of 51-54 Gy at the treating physicians discretion as long as dose constraints for normal tissues are met. The prescription dose to at least 95% of the PTV is 68 Gy using IMRT in 34 fractions, the mapped tumor (MT) boost region will receive an absolute dose of 76.5 Gy in 34 fractions. Assuming an α/β ratio of 3.0, this would be equivalent to 80 Gy in 2.0 Gy fractions.

Treatments usually are given 5 times per week. The bladder, rectum, penile bulb and urethra will be defined on the CT and MRI scans. Dose volume histogram (DVH) analysis will be used to assess plan acceptance per the RTOG guidelines. These include:

Rectum: Less than or equal to 35% and 55% of the rectum should receive \geq 65 Gy and \geq 40 Gy, respectively. A variation will be noted if up to an additional 10% of the rectal volume receives above the target doses specified. The inclusion of rectal volumes beyond these constraints will be considered a protocol violation. In many patients, these constraints may be easily met and every attempt should be made to achieve the best dose distribution possible.

Bladder: Less than or equal to 50% and 70% of the bladder (minus prostate bed CTV) should receive \geq 65 Gy and \geq 40 Gy, respectively. The criteria for the bladder have been relaxed because the dosimetric relationship of volume exposed to the specified marker doses is much less clear and the bladder neck is included in the CTV. A primary variation will be noted if up to an additional 7.5% of the bladder volume receives above the target doses specified. The inclusion of bladder volumes beyond these constraints will be considered a secondary protocol variation; it will not be considered a protocol violation. In some patients, the bladder will be relatively empty and the majority will be in the PTV.

4.7 Proteomic and Genomic Analyses of Blood

The objectives are to examine protein and single nucleotide polymorphisms in blood products for patterns that predict patient outcomes (e.g., prostate bed biopsy positivity, biochemical failure, and side effects). Blood samples will be collected according to the time points described in the Study Schedule (Appendix I). While these are exploratory studies, of key importance is to have such samples collected prospectively on a well-defined group of patients. Promoter hypermethylation is a common mechanism for tumor suppressor inactivation in human cancers and is a promising target for molecular detection of prostate cancer in blood (see section 4.10 on free circulating DNA in blood below).

4.8 Circulating Tumor Cells (CTCs) in Blood.

The objective is to capture CTCs in patients' peripheral blood samples and to study the CTCs for expression of biologically relevant protein markers by an immunocytochemical staining procedure. Peripheral blood will be collected in .5 ml SST plus blood collection tubes (BD Vacutainer). After 10 minutes, serum will be separated by centrifugation at 3500 rpm for 15 minutes at room temperature after which DNA will be extracted immediately. DNA will be extracted from 1 ml serum out using QIAamp UltraSens virus kit (Qiagen) following the manufacturer's protocol and stored at -20°C until further analysis. 5 ml from the anonymized blood samples will be used for CTC analysis, which includes enumeration and biomarker quantification.

We will test whether absolute pretreatment CTC counts and treatment-induced changes in CTC counts correlate with response to therapy as defined in sections 9.0 and 14.0. As a further validation of microfilter CTC capture, parallel samples will be analyzed using the currently-available FDA approved CTC collection platform, Veridex CellSearch. Blood samples will be collected at the time points

described in Study Calendar (Appendix I) or upon evidence of disease progression, whichever comes first.

Upon receipt, whole blood samples will be immediately diluted 1:1 in 1x PBS and 1% formalin for a final volume of 15ml, for 10 minutes at room temperature. Following partial fixation, blood is passed through the microfilter device using a syringe with steady low pressure. Following microfiltration, the filter will be disengaged from the device, and placed on a clean glass slide. 1uL drops of CureMount (Intrumedics) will be placed under each of the four corners of the microfilter. The microfilter and glass slide will be incubated under a UV lamp for 1-2 minutes. Our exclusive filter design enables higher CTC recovery as compared to the currently approved CellSearch technologies.[48] A clear advantage of our system is the ability to do cell analysis, including IF, directly on membrane. CTC will be defined as intact epithelial cells staining positive for cytokeratin and negative for CD45. Following UV crosslinking, the microfilters are subjected to IF. Total numbers of CTC will be counted and recorded by examining the entire area of the microfilter. At the same time, parallel samples will be collected and transported for overnight delivery to Quest Diagnostics, CA where CTC enumeration will be performed using the commercially available FDA approved CellSearch platform.

4.9 Free Circulating DNA (fcDNA) in Blood

Blood will be collected in 10 mL serum plus blood collection tubes (BD Vacutainer) at the time points described in the Study Calendar (Appendix I) or upon evidence of disease progression, whichever comes first. Serum will be separated by centrifugation at 3,500 rpm for 15 minutes at room temperature, after which DNA will be extracted immediately. DNA will be extracted from 1 mL serum using QIAamp UltraSens virus kit (Qiagen) following the manufacturer's protocol and stored at -20°C until further analysis.

Serum DNA will be quantified by real-time PCR for glutathione S-transferase, pi (GSTP1), based on the previous study by Bastian et al [29]. Amplification primers (forward, 5' AGG CCT TCG CTG GAG TTT C 3'; reverse, 5' CCA TGC TGG GAG CTC TGAG 3') and an amplicon-specific fluorogenic hybridization probe (6FAMCGC CGC AGT CTT CGC CACCTAMRA) will be used. The PCR will be carried out in an iCycler (Biorad). The PCR mixture will consist of 12.5 μ L of Taqman Universal master mix (Applied Biosystems), 5 pmoles of probe, and 5 pmoles each of the forward and reverse primer in a 25 μ L reaction volume. Each sample will be analyzed in triplicate. All PCR runs will include a negative control using water blanks. A standard curve will be generated for each PCR run using serial dilutions of human placental DNA (Sigma) at concentrations ranging between 160 ng/ μ L to 160 pg/ μ L. For calculation of DNA concentrations, the standard curve will be interpolated with the threshold cycle of unknown target samples.

4.10 Supportive Care Guidelines

All supportive therapy for optimal medical care will be given during the study period at the discretion of the managing physician(s) within the parameters of the protocol and documented. Most patients have grade 2 or lower urinary or bowel symptoms during and after treatment. Symptoms will be documented at least once a week as part of routine treatment clinic. In very rare cases, patients may experience extreme symptoms, such as urinary obstruction, diarrhea or significant bleeding requiring transfusion. Supportive measures, catheter placement and medication will be instituted as needed. Common supportive medications include:

- Antidiarrheals: Antidiarrheals, such as loperamide hydrochloride or diphenoxylate-atropine, may be used as needed. The amounts of the drug(s) and dates used should be documented as much as possible.

- Antispasmodics: Antispasmodics, such as oxybutynin or tolterodine tartrate, may be used as needed. The amounts of the drug(s) and dates used should be documented as much as possible.
- Alpha Blockers: Alpha blockers, such as doxazosin mesylate, terazosin hydrochloride or tamsulosin hydrochloride may be used as needed. The amounts of the drug(s) and dates used should be documented as much as possible.
- Analgesics: Analgesics is a broad category, including non-narcotic and narcotic agents. The use of non-narcotic agents, such as acetaminophen, non-steroidal anti-inflammatory agents or phenazopyridine hydrochloride for radiotherapy treatment-related pain should be documented as much as possible. Narcotic use as a consequence of treatment should also be recorded.
- Erectile Dysfunction: Erectile dysfunction may be treated with medical management (e.g., phosphodiesterase inhibitors), vacuum pumps or other devices as appropriate. The amounts of the drug(s) used and the dates that medical management or the use of mechanical devices was started should be documented.

4.11 Duration of Therapy

- The therapy will be delivered over approximately 7– 8 weeks.
- Treatment will be stopped for grade 4 acute toxicity (according to the current version of Common Terminology Criteria for Adverse Events (CTCAE version 4), but may be resumed per protocol if the treatment break is less than 10 working days. Since we have never observed grade 4 toxicity acutely using IMRT such an event is unlikely. If grade 4 toxicity resolves beyond the 10 days the treating physician will decide whether to give additional RT.
- Treatment will be stopped if metastasis is detected by radiographic or pathologic evidence and the patient will be removed from the study, but not from intent-to-treat analysis. A work-up for metastasis during treatment will only be carried out if the treating physician deems necessary.
- In case that the 2-year MRI exam identifies a suspicious for cancer lesion, US-guided biopsies will be taken.

5.0 CLINICAL AND LABORATORY EVALUATIONS

5.1 Baseline/Pretreatment Evaluations

Prior to Enrollment

- History and physical exam, including evaluation of patient's ability to perform daily activities (Zubrod performance status) within 8 weeks prior to protocol entry.
- Blood tests within 3 months prior to protocol entry or enrollment unless otherwise indicated. Up to five tubes of blood will be collected:
 - PSA level
 - Serum testosterone .
- Blood will be collected for research fluid testsBone scan if deemed necessary by treating physician obtained \leq 4 months prior to protocol entry or enrollment.
- DCE-MRI and or PET of prostate bed/pelvis at 1.5T or 3.0T MRI (preferably 3.0T) within 3 months prior to enrollment. Identifiable DCE-MRI tumor lesion or lesions. The enhancing lesion(s) in the prostate bed should be at least 0.4 cc and a maximum of 6 cc in total. (While PET may be used to identify GTV, MRI is still required for RT tx planning)
- A pathology review at the University of Miami of the outside biopsy material prior to enrollment.
- Psycho-Social Questionnaires:

- The Expanded Prostate Cancer Index Composite Questionnaire-SF12 (EPIC-SF12)
- Memorial Anxiety Scale for Prostate Cancer patients (MAX-PC)
- International Prostate Symptom Score (IPSS).

After enrollment and Prior to RT

- CT simulation.

5.2 Evaluations during Radiation Therapy

- Weekly history and physical including performance status (Zubrod), and toxicity.

5.3 Evaluations During the Last Week of Radiation Therapy

- History and physical including performance status (Zubrod), and toxicity.
- Blood (up to 5 tubes) will be collected:
 - PSAlevel I
 - Blood for research fluid tests
- Psychosocial questionnaires:
 - The Expanded Prostate Cancer Index Composite Questionnaire-SF12 (EPIC-SF-12)
 - Memorial Anxiety Scale for Prostate Cancer patients (MAX-PC)
- International Prostate Symptom Score (IPSS)

5.4 Post-treatment Evaluations

- History and physical, performance status (Zubrod), and toxicity at 6 weeks, 3 months, and then every 6 months for 5.25 years after completion of RT.
- Blood (up to 5 tubes) work in relation to RT:
 - PSA at 6 weeks, 3 months, and then every 6 months for 5.25 years.
 - Serum total testosterone 9 months after completion of RT.
 - Blood for research fluid tests will be collected at 3 months, 9 months and 2-2.5 years after completion of RT.
- DCE-MRI and or PET with timed contrast at 3 months, 9 months, and 2-2.5 years after completion of RT.
 - Should a lesion be identified, the treating physician will discuss management decisions with the participant
- Bone scan for a PSA of ≥ 2 or physician concern for metastasis.
- Psychosocial questionnaires will be administered at follow-up at 6 weeks, 3 months, 9 months, 15 months and yearly to 5.25 years:
 - Memorial Anxiety Scale for Prostate Cancer patients (MAX-PC).
 - The Expanded Prostate Cancer Index Composite Questionnaire-SF-12 (EPIC-SF12).

- International Prostate Symptom Scale (IPSS) will be done at each follow-up visit for 5.25 years. This includes 6 weeks, 3 months and every 6 months after RT for 5.25 years.

Note: Measurements and follow-up visits should occur within \pm 2 weeks up to the 3 months visit and within \pm 8 weeks for subsequent measurements/visits

5.5 Early Discontinuation of Therapy

See Criteria for Discontinuation of therapy in section 12.0.

6.0 DOSING DELAYS/DOSE MODIFICATIONS

6.1 Study Agent

The study agent in this protocol is radiation. The experimental component of the treatment is an MT boost of radiation delivered to the DCE-MRI-defined dominant region(s) by dose painting at 2.25 Gy per fraction. The MT boost region will receive an absolute dose of 76.5 Gy.

6.2 Other Agents

N/A

7.0 AGENT FORMULATION AND PROCUREMENT

N/A

8.0 CORRELATIVE/SPECIAL STUDIES

Isolation, quantification and staining of CTC's will be done. It is expected that over 30% of patients in the MAPS trial will have detectable CTC's. CTC levels will be obtained pretreatment and at the time of the 9-month blood draw at which time the endpoint PSA will be determined. The incidence and characteristics of the CTC's will be studied. Along these lines, fcDNA in serum will be quantified at both time points. We will test the relationship of baseline and endpoint obtained CTCs and fcDNA levels to biochemical complete response and nine months. The changes in CTC and fcDNA levels from baseline to the 9-month endpoint will be tested using paired t-test or signed rank test. Changes in the proportion of patients with levels above 180 ng/mL will be examined with McNemar's test.

9.0 MEASUREMENT OF EFFECT

The primary endpoint of the MAPS trial, referred to below as *PSA response rate*, is the proportion of study patients with PSA <0.1 ng/mL at 21 months after completion of study treatment. All patients will be evaluated for clinical or biochemical evidence of relapse as defined below. Section 14 provides further details with respect to quantitative endpoints.

9.1 Definitions

- *PSA response rate*: The proportion of study patients with PSA <0.1 ng/mL at 21 months after completion of study treatment.
- *Acute toxicity*: Toxicity occurring during treatment and within three months of completing treatment.
- *Late toxicity*: Toxicity occurring more than three months after treatment completion. *Failure rate*: The cumulative incidence of biochemical or clinical failure allowing for competing risk as needed. Clinical failure is defined as at least a 25% increase in the size of the tumor relative to the smallest volume recorded, or new extension of tumor beyond the capsule, or re-extension of tumor beyond the capsule after initial regression, or urinary obstructive symptoms with carcinoma found at TURP. Biochemical failure is defined as PSA \geq nadir + 2 ng/mL.

- *Failure-free Survival (FFS)*: The elapsed time from start of radiotherapy to first documented evidence of biochemical or clinical failure or death from any cause, whichever occurs first. In the absence of any event defining failure, follow-up time will be censored at the date of last documented failure-free status.
- *Overall Survival (OS)*: The elapsed time from start of radiotherapy to death from any cause. For surviving patients, follow-up will be censored at the date of last contact.
- *Biomarker expression*: Quantification of the amount of the biomarker specific immunohistochemical staining in the area of tumor.
- *QOL*: Two contemporary instruments will be utilized to assess patient function and bother (Expanded Prostate Cancer Index Composite-SF12 (EPIC-SF12) and prostate cancer-specific anxiety Memorial Anxiety Scale for Prostate Cancer patients (MAX-PC).

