14.1 Overview

This is a single-arm Phase II trial with the primary objective of determining whether MRI-targeted boost SRT (MTSRT) improves the rate of PSA response (i.e., PSA < 0.1 21 months post treatment completion) in men receiving radiation therapy due to rising PSA post-prostatectomy. Secondary objectives include evaluation acute and late occurring toxicity, quality of life, biochemical and clinical failure, and survival. Additionally, blood and biopsy tissue samples from study patients will provide data for various biomarker studies described in the Bankhead Coley Team Science project "Integrated biomarkers for individualized prostate cancer therapy".

A single stage design without interim analysis of the primary endpoint is proposed for this trial because it would not be practical or desirable to suspend accrual to accommodate an interim assessment of PSA response, which requires nine months follow-up. Moreover, PSA response is not a perfect near term surrogate for long term benefit and thus not a definitive basis for an early conclusion regarding efficacy. The trial involves standard therapy with dose escalation, and an evaluation of PSA response based on accrual of 40 evaluable patients will provide information needed to design a subsequent trial evaluating long term outcome. Early stopping rules based on monitoring the toxicity of study treatment are provided in Section 14.6.

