14.2 Sample size, accrual rate and study duration

Sample size is based on the primary objective of demonstrating that MTSRT increases the rate of PSA response to treatment, by which we mean undetectable PSA level (<0.1) when assessed 21 months after completing treatment. We expect the PSA response rate in the standard SRT to be 60%. [50] Assuming sufficient follow-up to determine PSA nine months post treatment, a total of 40 patients in the single-arm study provides 83.9% power to detect an absolute increase of 20% in the PSA response rate, from 60% to 80%, using a one-sided Fisher's exact test with 5% significance level. To ensure a minimum of 40 study patients evaluable for PSA response as our main study endpoint, we plan to enroll a total of 44 patients assuming 10% drop-out.

We plan to accrue 1 patient per month during the first year of this protocol. After the ramp-up phase is completed, we anticipate 1.5 patients per month. This rate was also calculated considering increasing prostate cancer volumes due to expansion of the department (anticipated growth at Sylvester main and Deerfield branch). Thus accrual will be complete in about 3 years; 12 in year 1 and 18 per year in year 2 and 3. Patients will be followed for a minimum of five years, giving total study duration of 8 years. The main efficacy endpoint will be analyzed after enrollment is complete and all patients have been

assessed for PSA response nine months post treatment, and a final efficacy analysis of all endpoints will be carried out at the conclusion of study when patients have been followed for 5 years. Analyses of some secondary endpoints, including acute toxicity, psychosocial parameters, and biomarker distribution on US guided biopsies, and initial MRI findings may be reported before the efficacy analyses. These secondary endpoints will be analyzed after all planned patients have been accrued, completed treatment and have a minimal potential follow-up of 3 months from the end of RT.

14.3 Definitions and endpoints:

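### The primary endpoint is defined at 21 months after treatment, but the power statement, evaluability rule and main-analysis trigger use nine months

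*Combined protocol and SAP*

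**What the plan says.** Four places set the endpoint at 21 months after treatment:

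- Section 9.0: the primary endpoint "is the proportion of study patients with PSA <0.1 ng/mL at 21 months after completion of study treatment".
- Section 9.1, the formal definition: "The proportion of study patients with PSA <0.1 ng/mL at 21 months after completion of study treatment".
- Section 14.1, the objective: whether the boost "improves the rate of PSA response (i.e., PSA < 0.1 21 months post treatment completion".
- Section 14.2, opening sentence: PSA response, "by which we mean undetectable PSA level (<0.1) when assessed 21 months after completing treatment".

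The operating rules for the same endpoint use nine months:

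- Section 14.1, on why there is no interim look: "interim assessment of PSA response, which requires nine months follow-up". Section 14.6 repeats this and there calls PSA response the primary efficacy endpoint.
- Section 14.2, power: "Assuming sufficient follow-up to determine PSA nine months post treatment, a total of 40 patients in the single-arm study provides 83.9% power".
- Section 14.2, main efficacy analysis: run once enrolment is complete and all patients have been "assessed for PSA response nine months post treatment".
- Section 14.3: both routes to being evaluable for efficacy, namely having the nine-month PSA, or failing or dying of prostate cancer within nine months.
- Section 14.5: the initial efficacy analysis follows the 9-month PSA.
- Section 8: the endpoint PSA is taken at the 9-month blood draw.

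Section 5.4 schedules PSA at 6 weeks, 3 months and every 6 months after that, so both a 9-month and a 21-month value are collected.

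**The concern.** One endpoint has two times in current text, and the time chosen decides when the data are cut, who is in the denominator and how a man is classified. A man below 0.1 ng/mL at month 9 and above it at month 21 is a responder under one set of passages and a non-responder under the other. The 60% reference rate, the 80% target and the 10% drop-out allowance are not tied to either time. In an open single-arm trial, leaving this unsettled also allows the time point to be chosen after results are known.

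**Working it through.** **1. The plan's own power figure.** Inputs from Section 14.2: n = 40, p0 = 0.60, p1 = 0.80, one-sided 5%. Using the exact one-sample binomial, the smallest cutoff r with P(X ≥ r | 40, 0.60) ≤ 0.05 is r = 30.

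- Exact alpha: P(X ≥ 30 | 0.60) = 0.0352.
- Power: P(X ≥ 30 | 0.80) = 0.8392, which matches the stated 83.9%.

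The arithmetic is correct. Time does not enter the formula, so the figure cannot show which time point was intended. The cutoff of 30 is derived here; the plan does not state it.

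**2. Men without a 21-month PSA at the main analysis.** Section 14.2 gives the rate: "After the ramp-up phase is completed, we anticipate 1.5 patients per month". The trigger is the last man reaching 9 months. Men enrolled in the 12 months before him (21 − 9 = 12) have then not reached 21 months, taking treatment duration as similar for all.

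- 12 × 1.5 = 18 men; 18/44 = 41%. With the limit of 40 given in Sections 3.0 and 14.0, 18/40 = 45%.
- The ±8-week visit window is about 1.84 months. At opposite extremes the lag is 12 ± 3.68, or 8.3 to 15.7 months; multiplied by 1.5 this gives about 12 to 24 men.

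**3. Section 14.3 set against Section 9.1.**

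| Man | 14.3 (nine months) | 9.1 (21 months) |
|---|---|---|
| 9-month PSA present, 21-month PSA absent | Evaluable by route 1 | No value to classify |
| Failure or prostate cancer death in months 9–21, no 21-month PSA | Outside the non-responder rule | No value to classify |
| 21-month PSA of 0.1 or more | Evaluable if route 1 is met | Non-responder; no gap |

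The gap is therefore limited to men without a 21-month value. Starting subsequent therapy before month 21 is also unaddressed, because Table 14.5 covers only time-to-event endpoints.

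**4. Sensitivity to the time point (assumed rates).** The documents give no rate specific to 9 or 21 months.

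| True rate at the time tested | P(X ≥ 30 of 40) |
|---|---|
| 50% | 0.1% |
| 55% | 0.7% |
| 60% | 3.5% |
| 65% | 12.1% |
| 70% | 30.9% |

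If both rates shift together and the cutoff is re-derived, power barely changes: 55% against 75% has cutoff 28, alpha 3.86% and power 82.1%; 50% against 70% has cutoff 26, alpha 4.03% and power 80.7%.

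**5. Drop-out by month 21 (assumed).** For 60% against 80%:

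- 15% of 44 lost: 44 × 0.85 = 37.4, so 37 evaluable; cutoff 28, alpha 3.48%, power 80.9%.
- 20% of 44 lost: 44 × 0.80 = 35.2, so 35 evaluable; cutoff 27, alpha 2.60%, power 74.5%.
- For comparison, n = 36 gives 83.2%, so much of the drop at 35 comes from the discreteness of the exact test.

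**The case against.** Section 14.3 refers to Section 9.1 for endpoint definitions, which could make 21 months govern and the nine-month wording out of date. Section 14.5 calls the nine-month look initial, and a final analysis of all endpoints follows at five years, when every available 21-month PSA will exist. On that reading the endpoint is mistimed but not lost. This softens the point without removing it. Section 9.0 in turn refers to Section 14 for further detail, Section 14.2 analyses its main efficacy endpoint at nine months, and no analysis is scheduled for month 21.

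Several narrower objections do stand:

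- The two evaluability gaps overlap. A man with a 9-month PSA who fails later is already evaluable by route 1, and what he lacks is the 21-month value. He could also be read as simply outside the numerator, but the plan does not say so.
- The missing rule on subsequent therapy would exist at nine months too.
- The cutoff of 30 rests on the one-sided test. Section 14.5 states two-sided tests, and the two-sided exact 95% interval for 30/40 has a lower limit of 58.8%. Excluding 60% then needs 31/40 (lower limit 61.5%), with power 73.2%; the 12.1% and 30.9% above become 6.4% and 19.6%.
- The assumed rates and drop-out levels have no support in the documents in either direction.

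None of these settles which time point is primary.

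**Conclusion.** The concern holds, and it must be fixed before analysis. The contradiction is in current text and is wrong as written, not merely incomplete. Followed literally, the plan triggers its main efficacy analysis up to 12 months before the last men's defining PSA exists. That affects about 18 of 44 men if accrual runs at the projected rate and visits fall on schedule. It also leaves men without a 21-month value with no stated outcome. No power loss is claimed. The effect on error rates depends on the unknown difference between the 9- and 21-month response rates, so those figures are illustrative only.

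**What to change.** Choose one time point before analysis and use it in 9.0, 9.1, 14.1, 14.2, 14.3 (both routes), 14.5 and 14.6. State that the 60% and 80% rates and the 10% drop-out apply at that time, or restate the power. Make PSA response at the other time a named secondary endpoint.

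- **If 21 months is kept:** run the primary analysis when the last man's 21-month PSA is due, and extend both 14.3 routes to 21 months. State how men with no 21-month PSA, or with subsequent therapy before it, are counted. In Section 8, remove the statement that the endpoint PSA is determined at the 9-month draw, and tie the remaining nine-month response wording to the secondary endpoint. Cost: no new visit (3, 9, 15, 21 months are already scheduled), a readout about 12 months later, and drop-out that may exceed 10%.
- **If nine months is chosen:** change 9.0, 9.1 and the first sentences of 14.1 and 14.2. Cost: text only, with no operational change, though it does replace the formally defined primary endpoint and should be recorded as such.

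Either way, the circulating tumour cell and free DNA draw in Section 8 stays at 9 months, because research blood is scheduled at 3 months, 9 months and 2–2.5 years.
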